
8.1 Screening

Screening activities ([Table 8-1](#)) must be initiated only after the ICF (and assent if applicable) has been signed. A participant may go directly from the screening visit to the baseline visit, if they meet the criteria, as outlined in [Section 3.1](#). In this case the screening period may last up to 14 days. If the time between the screening labs and randomization is less than or equal to 7 days, then the labs do not need to be repeated and the screening labs will function as both the screening and baseline labs.

A participant who enters screening but is determined not eligible will be considered a screen failure. The investigator may consider re-screening the participant at a later time if he/she believes that the participant's condition has changed and they may potentially be eligible. In this case, a new participant number will be allocated to the participant and he/she will need to re-perform all Screening Visit procedures. A participant may be re-screened once. A minimum of 2 weeks must elapse between screen failure and re-screening. The participant must provide new written informed consent before being re-screened.

8.1.1 Information to be collected on screening failures

Participants who sign an ICF and subsequently found to be ineligible prior to randomization will be considered a screen failure. The reason for screen failure should be recorded on the appropriate eCRF. The demographic information, informed consent, reported AEs related to Auxiliary Medicinal Product (AxMP) and Inclusion/Exclusion pages must also be completed for screen failure participants. No other data is required to be entered into the clinical database for participants who are screen failures, unless the participant experienced a SAE during the screening period (see SAE [Section 10.1.3](#) for reporting details). If the participant fails to be randomized, the IRT must be notified within 2 days of the screen fail that the participant was not randomized.

Participants who are randomized and fail to start treatment, e.g. participants randomized in error, will be considered an early terminator. The reason for early termination should be recorded on the appropriate eCRF.

8.2 Participant demographics/other baseline characteristics

Country-specific regulations should be considered for the collection of demographic and baseline characteristics in alignment with eCRF.

Participant demographic and baseline characteristic data to be collected on all participants include: age, sex, race, ethnicity, relevant medical history, CV disease history, alcohol history, COVID-19 vaccination information and current medical condition present before informed consent was signed (where possible, diagnoses and not symptoms will be recorded), concomitant LLT, as well as relevant laboratory tests.

Participant race and ethnicity are collected and analyzed to assess the diversity of the study population as required by certain Health Authorities and may be used to identify variations in safety or efficacy due to these factors.

All prescription medications, over-the-counter drugs and significant non-drug therapies prior to the start of the study must be documented. See the protocol [Section 6.2.1](#) Concomitant Therapy for further details on what information must be recorded on the appropriate eCRF page.

Investigators will have the discretion to record abnormal test findings on the medical history eCRF whenever, in their judgment, the test abnormality occurred prior to the informed consent signature

The investigator will record in the eCRF in which cardiovascular risk category the participants is allocated at screening, run-in period (if applicable) and during the treatment period for analysis purpose, and also in IRT at screening for stratification.

8.3 Efficacy

The LDL-C and other exploratory biomarker assessments are specified below, with the Assessment Schedule ([Table 8-1](#)) detailing when each assessment is to be performed. Participants will be in a fasted state for all of these laboratory assessments. Details regarding the collection, processing, shipping and storage of the samples for central lab will be provided in a Laboratory Manual.

8.3.1 LDL Cholesterol

The primary efficacy assessment will be LDL-C, as tested and reported by the central lab as part of the full Lipid Panel at the frequency shown in [Table 8-1](#).

In addition, where a recent LDL-C measurement is required in order to decide for LLT escalation, LDL-C will be measured locally at sites using a LDL-C point of care device at the frequency shown in [Table 8-1](#). In the event the assessment cannot be completed with the LDL-C point of care device, the LDL-C is to be assessed by the central lab.

Participants need to be fasting for all LDL-C assessments. LDL-C values will not be blinded for the investigator to enable an ongoing individual optimization of LLT if necessary to achieve a participant's LDL-C target. The investigator is encouraged to not disclose the LDL-C value to the participant.

If participants gain eligibility and receive LDL-apheresis in the course of study (refer to [Section 3.4](#)), LDL-C must be measured immediately before the scheduled apheresis treatment.

8.3.2 Appropriateness of efficacy assessments

Inclisiran is a siRNA which acts to reduce LDL-C. LDL-C is a well-defined and validated laboratory parameter and is routinely assessed in clinical trials. LDL-C reduction is an accepted surrogate for CV risk reduction, e.g. for statins and PCSK9- blocking monoclonal antibodies. While multiple factors contributing to the development of ASCVD have been described, strong and consistent evidence from genetics, epidemiology, Mendelian randomization studies and randomized trials, have established that LDL-C is not only a laboratory parameter of increased risk, but also a causal and modifiable factor in ASCVD ([Ference et al 2017](#)). Laboratory tests related to the endpoints are in line with the expected efficacy of inclisiran. It is the primary endpoint of the study.

Exploratory endpoints are hypothesis generating and exploratory in nature.

8.4 Safety

The safety profile of inclisiran has been well characterized in the Phase III LDL-C lowering studies (ORION-9, -10 and -11) ([Wright et al 2021](#)) which included over 3,600 participants with similar demographic and baseline characteristics to the population expected to be included in the current study.

The safety profile of rosuvastatin has been well characterized and is outlined in the local SmPC.

As per [Section 4.6](#), during a Public Health emergency as declared by Local or Regional authorities i.e. pandemic, epidemic or natural disaster, that limits or prevents on-site study visits, regular phone or virtual calls can occur (every 4 weeks or more frequently if needed) for safety monitoring and discussion of the participant's health status until it is safe for the participant to visit the site again.

Safety assessments are specified below with the Assessment Schedule detailing when each assessment is to be performed.

For details on AE collection and reporting, refer to the AE [Section 10.1](#).

A complete physical examination will be performed at the visits, as outlined in [Table 8-1](#). Details on what is included in the complete physical exam and the requirements to perform vital signs assessment and height/ weight measurements are provided in [Table 8-2](#).

Table 8-2 Assessments & Specifications

Assessment	Specification
Physical examination	A complete physical examination will include the examination of general appearance, skin, neck (including thyroid), eyes, ears, nose, throat, lungs, heart, abdomen, back, lymph nodes, extremities, vascular, and neurological. If indicated based on medical history and/or symptoms, rectal, external genitalia, breast, and pelvic exams will be performed. Information for all physical examinations must be included in the source documentation at the study site. Clinically relevant findings that are present prior to signing informed consent must be recorded on the appropriate eCRF that captures medical history. Significant findings made after signing informed consent which meet the definition of an AE must be recorded as an AE.
Vital signs	Vital signs include blood pressure (BP) and pulse measurements. After the participant has been sitting for five minutes, with back supported and both feet placed on the floor, systolic and diastolic blood pressure will be measured three times using an automated validated device with an appropriately sized cuff. The repeat sitting measurements will be made at 1 - 2 minute intervals and the mean of the three measurements will be used. In case the cuff sizes available are not large enough for the participant's arm circumference, a sphygmomanometer with an appropriately sized cuff may be used.
Height and weight	Height in centimeters (cm) and body weight (to the nearest 0.1 kilogram (kg) in indoor clothing, but without shoes) will be measured.

8.4.1 Laboratory evaluations

As per [Section 4.6](#), during a Public Health emergency as declared by Local or Regional authorities, i.e. pandemic, epidemic or natural disaster, that limits or prevents on-site study visits, if participants cannot visit the site for protocol specified safety lab assessments, an alternative lab (local) collection site may be used.

Specimens will be obtained at the time points detailed in the Assessment Schedule (Table 8-1). Details on what is included in hematology, chemistry, lipids/lipoproteins and urinalysis laboratory evaluations are provided in Table 8-3.

Central laboratory will be used for analysis of all specimens collected, with the exception of urine pregnancy tests, which will be done locally (using testing materials supplied by the central laboratory). Serum pregnancy tests at screening will be done by the central laboratory.

For immediate and local action on statin up/down-titration or other LLT escalation, LDL-C value will be measured using a LDL-C point of care device and recorded in the eCRF accordingly. In the event the assessment cannot be completed with the LDL-C point of care device, the LDL-C is to be assessed by the central lab.

LDL-C will also be centrally analyzed at the visits as outlined in Table 8-1, as part of the full Lipid Panel.

Details on the collections, shipment of samples and reporting of results by the central laboratory are provided to investigators in a Laboratory Manual.

Clinically significant abnormalities must be recorded as either medical history/current medical conditions or AEs as appropriate.

Table 8-3 Laboratory Assessments

Test Category	Test Name
Hematology	Hematocrit, Hemoglobin, Red Blood Cell (RBC) Count, Mean Corpuscular Volume (MCV), Mean Corpuscular Hemoglobin (MCH), Mean Corpuscular Hemoglobin Concentration (MCHC), Platelets, Erythrocyte Cell Morphology*, White Blood Cell (WBC) count with Differential (Basophils, Eosinophils, Lymphocytes, Monocytes, Neutrophils, Bands**)
Chemistry	Full chemistry: AST, ALT, ALP, GGT, total bilirubin, direct and indirect bilirubin (if total >2ULN), CK, creatinine, creatinine clearance, eGFR*, sodium, potassium, chloride, glucose (fasting)***, HbA _{1c} *** Limited chemistry: ONLY: AST, ALT, ALP, GGT, total bilirubin (fractioned bilirubin (if total bilirubin >2ULN), CK
Lipids/Lipoproteins/Biomarkers	LDL-C, ApoB, Lp(a), non-HDL-C, total cholesterol, triglycerides, and HDL-C. PCSK9 levels, see Table 8-1.
Pregnancy Test	Serum / Urine pregnancy test (see Section 8.4.3)
Urinalysis	Dipstick measurements for: specific gravity, pH, glucose, protein (total), ketones, bilirubin, urobilinogen, nitrite, hemoglobin (blood), leukocytes esterase If dipstick measurement results are positive (abnormal), microscopic examination will be performed

*Reflex testing only in event of abnormal result from absolute count/ differentials

**eGFR will be calculated using the Modification of Diet in Renal Disease (MDRD) eGFR formula as follows:
 $175 \times [\text{standardized serum creatinine (mg/dL)}]^{-1.154} \times [\text{age}]^{-0.203} \times [1.212 \text{ if race=black/African American}] \times [0.742 \text{ if female}]$

***Diagnosis of diabetes based on HbA_{1c} \geq 6.5% (48 mmol/mol) or FPG two consecutive values \geq 126 mg/dL (7.0 mmol/L).

8.4.2 Electrocardiogram (ECG)

Not Applicable.

8.4.2.1 Cardiac imaging - MRA (magnetic resonance angiography), MUGA (multiple gated acquisition) scan or echocardiogram

Not Applicable.

8.4.2.2 Cardiac enzymes

Not Applicable.

8.4.3 Pregnancy

Women of child-bearing potential, defined as all women physiologically capable of becoming pregnant, unless they are using highly effective methods of contraception while taking study treatment, which includes rosuvastatin, and for 5 days (= 5 times the terminal half-life) of rosuvastatin) after stopping medication. Highly effective contraception methods include:

- Total abstinence (when this is in line with the preferred and usual lifestyle of the participant. Periodic abstinence (e.g. calendar, ovulation, symptothermal, post-ovulation methods) and withdrawal are not acceptable methods of contraception.
- Female sterilization (have had surgical bilateral oophorectomy with or without hysterectomy), total hysterectomy, or bilateral tubal ligation at least six weeks before taking study treatment. In case of oophorectomy alone, only when the reproductive status of the woman has been confirmed by follow up hormone level assessment.
- Male sterilization (at least 6 months prior to screening). For female participants on the study, the vasectomized male partner should be the sole partner for that participant
- Use of oral, (estrogen and progesterone), injected, or implanted hormonal methods of contraception or placement of an intrauterine device (IUD) or intrauterine system (IUS), or other forms of hormonal contraception that have comparable efficacy (failure rate < 1%), for example hormone vaginal ring or transdermal hormone contraception.

In case of use of oral contraception women should have been stable on the same pill for a minimum of 3 months before taking study treatment.

Women are considered post-menopausal if they have had 12 months of natural (spontaneous) amenorrhea with an appropriate clinical profile (e.g. age appropriate history of vasomotor symptoms). Women are considered not of childbearing potential if they are post-menopausal or have had surgical bilateral oophorectomy (with or without hysterectomy), total hysterectomy or bilateral tubal ligation at least six weeks ago. In the case of oophorectomy alone, only when the reproductive status of the woman has been confirmed by follow up hormone level assessment is she considered not of childbearing potential.

If local regulations deviate from the contraception methods listed above to prevent pregnancy, local regulations apply and will be described in the local ICF.

All woman of child-bearing potential will have a serum pregnancy test performed at the Screening Visit. A urine pregnancy test will be performed at all subsequent visits. A positive urine pregnancy test should be confirmed with a serum pregnancy test. Participants with a positive urine/serum pregnancy at any time in the study must be excluded.

Additional pregnancy testing might be performed if requested by local requirements.

As per [Section 4.6](#), during a Public Health emergency as declared by Local or Regional authorities i.e. pandemic, epidemic or natural disaster, that limits or prevents on-site study visits, if participants cannot visit the site, urine pregnancy test kits may be used at the participant's home. Relevant participants can perform the urine pregnancy test at home and report the result to the site. It is important that participants are instructed to perform the urine pregnancy test first and only if the test result is negative proceed with the administration of the study treatment. A communication process should be established with the participant so that the Site is informed and can verify the pregnancy test results (e.g., following country specific measures).

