9.1 Discontinuation from study treatment and from study

9.1.1 Discontinuation from study treatment

Discontinuation of study treatment for a participant occurs when study treatment is permanently stopped for any reason (prior to the planned completion of study drug administration, if any) and can be initiated by either the participant or the investigator.

The investigator must discontinue study treatment (inclisiran/placebo) or rosuvastatin for a given participant if, he/she believes that continuation of the respective study treatment would negatively impact the participant's well-being.

Discontinuation from study treatment (inclisiran/placebo) or rosuvastatin is required under the following circumstances:

- Participant/guardian decision.
- Pregnancy.
- Use of prohibited treatment as per recommendations in the prohibited treatment ([Section 6.2.2](#)).
- Any situation in which continued study participation might result in a safety risk to the participant ([Section 10.2](#)).

- Following emergency unblinding.
- Any laboratory abnormalities that in the judgment of the investigator, taking into consideration the participant's overall status, prevents the participant from continuing participation in the study ([Section 10.2](#)).
- Participant is switched to a PCSK9 mAb ([Section 3.4](#)).
- Intractable cases with LDL-C still too high after the recommended LLT escalation ([Figure 3-2](#) of [Section 3.4](#)) and participant is required to be treated per local standard of care.

If a participant is required to discontinue from Inclisiran/Placebo, they should remain on open label study treatment (rosuvastatin) and continue following the protocol recommended escalation scheme as applicable ([Section 3.4](#) and assessment schedule ([Table 8-1](#)).

If a participant is required to discontinue from open label treatment rosuvastatin, they should be switched to an alternative well tolerated statin, as per local standard of care and at the discretion of the investigator, and continue following the protocol recommended LLT escalation scheme as applicable ([Section 3.4](#)) and assessment schedule ([Table 8-1](#)).

If discontinuation from study treatment occurs, the investigator should make a reasonable effort to understand the primary reason for the participant's discontinuation from study treatment and record this information in eCRF.

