Participants who discontinue from study treatment (Inclisiran/placebo) or rosuvastatin should be followed-up and return to the visits as outlined in the Assessment Schedule ([Table 8-1](#)), or at a minimum agree to return for the end of study visit or have the safety phone call indicated in the Assessment Schedule (refer to [Table 8-1](#)).

If the participant cannot or is unwilling to attend any visit(s), the site staff should maintain regular telephone contact with the participant, or with a person pre-designated by the participant. This telephone contact should preferably be done according to the study Assessment Schedule.

The investigator must also contact the IRT to register the participant's discontinuation from study treatment (for inclisiran/placebo only).

If discontinuation occurs because treatment code has been broken, please refer to Emergency breaking of treatment code section.

In case a participant discontinues blinded investigational treatment inclisiran/placebo due to a switch to PCSK9 mAb (refer to [Section 3.4](#)), the participant will remain in the study and be followed-up until the participant's end of study according to the Assessment Schedule.

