10.1.4 Pregnancy reporting

Pregnancies

If a trial participant becomes pregnant, the study treatment should be stopped, and the pregnancy consent form should be presented to the trial participant. The participant must be given adequate time to read, review and sign the pregnancy consent form. This consent form is necessary to allow the investigator to collect and report information regarding the pregnancy. To ensure participant safety, each pregnancy occurring after signing the informed consent must be reported to Novartis within 24 hours of learning of its occurrence. The pregnancy should be followed up to determine outcome, including spontaneous or voluntary termination, details of the birth, and the presence or absence of any birth defects, congenital abnormalities, or maternal and/or newborn complications.

Pregnancy should be recorded and reported by the investigator to the Novartis Chief Medical Office and Patient Safety (CMO&PS). Pregnancy follow-up should be recorded on the same form and should include an assessment of the possible relationship to the study treatment and pregnancy outcome. Any SAE experienced during pregnancy must be reported.

After consent is provided, the pregnancy reporting will continue for up to one year after the estimated date of delivery.

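### Protocol sections 8.4.3, 9.1.1 and 10.1.4 give inconsistent instructions for a participant who becomes pregnant after randomisation, both on study status and on statin treatment

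*Protocol*

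**What the plan says.** Four places in the protocol bear on a positive pregnancy test after randomisation.

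- **Section 8.4.3 (Pregnancy):** "Participants with a positive urine/serum pregnancy at any time in the study must be excluded". Table 8-1 schedules urine tests for women of child-bearing potential at the treatment visits through Day 360, so the sentence applies well beyond screening.
- **Section 10.1.4 (Pregnancy reporting):** "If a trial participant becomes pregnant, the study treatment should be stopped". The pregnancy is then followed to its outcome under a separate consent. Leaving the study is not mentioned.
- **Section 9.1.1 (Discontinuation from study treatment):** "Discontinuation from study treatment (inclisiran/placebo) or rosuvastatin is required under the following circumstances", and pregnancy is on the list that follows. Two general instructions come next. Whoever must stop the injection is told that "they should remain on open label study treatment (rosuvastatin) and continue following the protocol recommended escalation scheme as applicable". For whoever must stop rosuvastatin, "they should be switched to an alternative well tolerated statin, as per local standard of care and at the discretion of the investigator". On visits: "Participants who discontinue from study treatment (Inclisiran/placebo) or rosuvastatin should be followed-up and return to the visits as outlined in the Assessment Schedule", with an end-of-study visit or the safety call as the minimum.
- **Sections 3.4 and 8:** participants who stop study treatment early stay in the study and are followed to its end.

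The SAP has no separate rule for pregnancy.

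**The concern.** A site with a positive test on its hands needs two answers: is the participant still in the study, and which lipid-lowering drugs stop? The protocol gives more than one answer to each.

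For a product that participants must be told may carry unknown risk to the fetus (sections 4.5 and 7), the stopping instruction should not depend on which section a site opens first. What is at stake is uniform handling of participant safety across sites. A lesser consequence is that scheduled visits after the event might be kept at one site and dropped at another.

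**Working it through.** No arithmetic decides this point. It was checked by setting the passages side by side.

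**Study status**

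1. Can the 8.4.3 sentence be read as eligibility wording only? Not easily. Exclusion criterion 24 already covers pregnancy at screening and baseline, while 8.4.3 applies throughout the study.
2. Does *excluded* have a defined meaning? No. The glossary defines discontinuation from study treatment (assessments continue) and discontinuation from study (assessments stop). Section 8.4.3 uses neither term. Removal from the study is the natural reading.
3. Sections 3.4, 8 and 9.1.1 point the other way: stopping treatment does not end participation. Section 10.1.4 is silent on participation.

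**Statin treatment**

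1. Under section 10.1.4, study treatment stops. The glossary includes background therapy in that term, and 8.4.3 and exclusion criterion 25 name rosuvastatin as part of it. On those definitions rosuvastatin stops too.
2. The protocol also uses the same term in a narrower sense: sections 3.4, 6.1.1 and 9.1.1 gloss it as the injection alone. A site reading 10.1.4 in that sense would stop only the injection.
3. Section 9.1.1 joins the two products with *or* and does not say which one pregnancy stops, or whether both do.
4. If the injection stops, the next sentence of 9.1.1 keeps her on rosuvastatin. If rosuvastatin stops, the sentence after that moves her to another statin. Neither sentence exempts pregnancy.
5. Where the authors meant both products they said so explicitly, in section 4.1.1 (intractable cases) and in the action column of Table 6-3. The pregnancy rule has no such wording.

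**How many participants could still be affected**

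Amendment 3 reports 1776 randomised and 1391 with treatment completed on 2 September 2024. At most 1776 − 1391 = 385 were still on treatment, less an unstated number who had already discontinued. The last participant started on 26 February 2024, so that participant's Day 360 is 359 days later, 19 February 2025. The rules therefore still applied to some participants when Amendment 3 was issued. The share of child-bearing potential is not given.

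**Effect on the analysis**

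If she leaves the study, no data exist after the event. SAP sections 2.5.3 and 5.5.3 then impute jump-to-reference values in the inclisiran arm and missing-at-random values in the placebo arm. If she stays, observed values are used. Only a pregnancy before the Day 90 assessment could touch the primary endpoint. The Day 90 lipid window closes at Day 120 (SAP Table 2-1), which for the last participant is 119 days after 26 February 2024, or 24 June 2024. A change to the text after that date cannot affect the primary endpoint.

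**The case against.** The best defence is that the specific rule governs the general one. Section 10.1.4 is the pregnancy-specific text, it stops study treatment, and the definitions make that include rosuvastatin. The statin sentences in 9.1.1 are follow-ons to every listed reason, and the switch sentence defers to local standard of care and investigator discretion. Section 9.1.1 also obliges the investigator to stop either product if continuing would harm the participant. A careful investigator would probably reach a sensible answer.

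Much of this stands, and it limits what can be claimed. A reader might infer any of the following, which the documents do not support:

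- **That the protocol directs pregnant participants to stay on a statin.** It does not. Pregnancy is a listed reason for discontinuation. The fault is an unclear *or* and a missing exception.
- **That removal ends safety collection.** It does not. Section 9.3 provides a safety call at least 90 days after last study treatment in case of early study discontinuation. Section 10.1.3 requires serious adverse event reporting until 30 days after the last visit. Section 10.1.4 continues pregnancy reporting, after consent, up to one year after the estimated delivery date. What could be lost is the scheduled LDL-C and questionnaire visits.
- **That visits after stopping treatment are compulsory.** Section 9.1.1 says *should* and gives a minimum fallback.
- **That the primary estimand is undermined.** Treatment policy uses data collected after discontinuation where they exist, and the SAP specifies the imputation where they do not.
- **That exclusion criterion 24 conflicts with these rules.** It applies only at screening and baseline.

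The defence does not remove the inconsistency. It relies on sites choosing the broader of two meanings of study treatment and overriding two unqualified sentences in 9.1.1. It also leaves the meaning of *excluded* in 8.4.3 unresolved.

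**Conclusion.** The inconsistency is real and has two parts: whether she remains in the study, and which lipid-lowering treatments stop. Sites that follow the text in good faith can reach opposite answers on either.

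The number affected is probably small. That is a judgement from a population at high or very high cardiovascular risk, many of whom will not be of child-bearing potential; the documents give no expected number of pregnancies. On the same basis the effect on the endpoints is negligible. The point deserves correction because it concerns participant safety and is cheap to fix, not because it threatens the trial's conclusions. The finding rests on reading *excluded* as removal from the study, which is the natural but not the only possible reading. It takes no position on which clinical rule is right.

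**What to change.** Reconcile sections 8.4.3, 9.1.1 and 10.1.4 so that together they give one instruction on three matters:

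1. which study treatments stop on a positive test, naming the injection and rosuvastatin separately;
2. whether the two general statin sentences in 9.1.1 apply to pregnancy;
3. whether *excluded* in 8.4.3 means ineligibility, discontinuation of study treatment or discontinuation from study, replaced by the protocol's defined term.

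The clinical content is for the sponsor to decide. The cost is a few sentences in an amendment and a letter to sites. No procedure is added, and the SAP need not change, since it already covers both the followed-up and the missing-data case.
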